6.2.1.2 Breaking the treatment blind in an emergency situation

In the event of an emergency, it will be possible to determine to which treatment arm and dose the study participant has been allocated by contacting the IRT. At the start of the study, all sites will be provided with details of how to contact the system for code breaking. The Medical Monitor or equivalent should be consulted prior to unblinding, whenever possible.

The CPM will be informed immediately via the IRT when a code is broken but will remain blinded to specific treatment information. Any unblinding of the IMP performed by the investigator must be recorded in the source documents and on the Study Termination eCRF page.

6.3 Treatment compliance

During the Treatment Period, IMP will be administered at the clinical site or study participant's home as a sc infusion by a qualified designee. Drug accountability must be recorded on the Drug Accountability form (see Section [6.1.1](#)).

6.4 Concomitant medication(s)/treatment(s)

6.4.1 Permitted concomitant treatments (medications and therapies)

The following concomitant medications are permitted during the study and if possible, kept stable for the duration of the study (Table 6-2):

Table 6-2: Permitted concomitant treatments (medications and therapies)

Permitted Medications	Dose	Comment ^a
Oral corticosteroids	≤20mg/day (prednisone equivalent dose)	Stable dose for █████ prior to Baseline
Mycophenolate mofetil	≤3g/day	Stable dose for █████ prior to Baseline
Cyclosporin	≤5mg/kg/day for unmodified ≤4mg/kg/day for modified	Stable dose for █████ prior to Baseline
Azathioprine	≤3mg/kg/day	Stable dose for █████ prior to Baseline
Danazol	≤15mg/kg/day	Stable dose for █████ prior to Baseline
Dapsone	100mg/day	Stable dose for █████ prior to Baseline
Eltrombopag, Avatrombopag	Any dose	Stable dose for █████ prior to Baseline
Fostamatinib	Any dose	Stable dose for █████ prior to Baseline

^a Stable dose is defined as either the same dose and frequency of the respective medication taken for the period of time defined in Table 6-2, or no dose of the respective medication taken for the period of time as defined in Table 6-2.

The use of medicinal cannabidiols and medicinal marijuana (prescribed by a physician) is also permitted. When applicable, the study participant must be on a stable dose of cannabidiols and/or medicinal marijuana for █████ prior to Screening and remain stable for the duration of the study. For **Japan**-specific regulations, see Appendix 8, Section 10.8.

6.4.2 Prohibited concomitant treatments (medications and therapies)

The following concomitant medications are prohibited during the study:

- IVIg (unless given as a rescue therapy)
- All biologics including rituximab
- Cyclophosphamide
- Pimecrolimus
- PEX
- Immunoabsorption

- Anti-D
- Any systemically administered corticosteroids above the allowed background dose (unless required as a rescue therapy)
- Romiplostim
- Vinca alkaloids (vincristine, vinblastine)
- Anticoagulants and antiplatelets (warfarin, heparin, clopidogrel, aspirin [enteric coated up to 150mg daily allowed], salicylics, dipyridamole, prasugrel, ticagrelor, tirofiban, and abciximab).

For study participants who require a medical or surgical procedure that requires the use of general anesthesia, discussion must occur prior to the procedure with the Medical Monitor or study physician, such that a decision on the participant's continued participation in the study can be made. In an emergency situation, the discussion should occur as soon as possible after the procedure.

The use of prohibited concomitant treatment will lead to permanent discontinuation from IMP. Study participants should then complete the assessments outlined for the Early Withdrawal (EW) Visit and enter the SFU Period.

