12. Study participant has experienced a clinically symptomatic GI bleed (positive hemocult tests without any signs and symptoms of GI bleeding will **not** be considered as "clinically symptomatic") in the last 6 months prior to the Screening Visit and/or has current gastritis or esophagitis and/or has a known risk for clinically relevant GI bleeding beyond ITP.
13. Study participant has experienced intracranial bleed in the last 6 months prior to the Screening Visit.
14. Study participant has a history of coagulopathy disorders other than ITP.
15. Criterion removed.
16. Splenectomized participant with past medical history of OPSI.
- 17a. Study participant with current or medical history of IgA deficiency, or a measurement of IgA <50mg/dL at the Screening Visit.

Prior/Concomitant therapy/procedures

18. Study participant who has received any blood or blood products within 2 weeks prior to the Baseline Visit.
19. Study participant has undergone a splenectomy in the 2 years prior to the Baseline Visit.
- 20b. Splenectomized participant without adequate vaccination against *S. pneumoniae*, *N. meningitidis*, and *H. influenzae* as evidenced by:
 - a lack of documented vaccination records per local guidance, OR
 - have not completed required vaccinations (*S. pneumoniae*, *H. influenzae*, and *N. meningitidis*) per Section 8.2.6 during the Prolonged Screening Period

Note: For splenectomized participants without any prior vaccination against one or all of the above-mentioned bacteria please refer to Section 8.2.6 of the protocol.

For **Japan**-specific regulations, see Appendix 8, Section 10.8.

- 21a. Study participant has received a live vaccination within 8 weeks prior to Day 1 (Baseline Visit); or intends to have a live vaccination during the course of the study or within 7 weeks following the final dose of IMP.
22. Criterion removed.
- 23a. Criterion removed.
- 24a. Study participant has been treated with prohibited immunosuppressants, biologics and other therapies within a timeframe shorter than detailed in [Table 5-1](#). Medications as presented in [Table 5-1](#) are prohibited during the study, unless required as rescue therapy (specified in [Section 6.4.3](#)) during the study.

Table 5-1: Treatment-free periods for immunosuppressants, biologics, other therapies, and antiplatelet/anticoagulant agents

Generic name (commercial/trade name)	Period relative to Baseline Visit (regardless of route of administration)
Immunosuppressants	

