Cyclophosphamide	6 months
Pimecrolimus (Elidel [®])	4 weeks
Vinca alkaloids (vincristine, vinblastine)	12 weeks
Biologics (monoclonal antibodies and fusion proteins)	
Abatacept (CTLA 4-Ig) (Orencia [®])	6 months
Belimumab (Benlysta [™])	6 months
Golimumab (Simponi [™])	6 months
Natalizumab (Tysabri [®])	6 months
Ofatumumab (Arzerra [®])	6 months
Rituximab (Rituxan [®]) and ocrelizumab	6 months or if more than 6 months and B cells have not returned to normal
TACI-Ig (Atacicept [®])	10 months
Veltuzumab	6 months
Other biologics	3 months or within 5 half-lives prior to the Baseline Visit (whichever is longer)
Inebulizumab	6 months and B-cell counts are within normal range
Other	
Intravenous immunoglobulin	4 weeks
Plasma exchange (PEX)	4 weeks
Anti-D	4 weeks
Romiplostim (Nplate [®])	4 weeks

Generic name (commercial/trade name)	Period relative to Baseline Visit (regardless of route of administration)
Antiplatelets and Anticoagulants (eg, thrombin inhibitors, Vitamin K antagonists, factor inhibitors)^a	
Warfarin	2 weeks
Phenprocoumon	2 weeks
Acenocoumarol	2 weeks
Heparin	1 week
Clopidogrel	1 week
Salicylates (Aspirin)	1 week (enteric coated aspirin up to 150mg daily allowed)
Dipyridamole	1 week
Prasugrel	1 week
Ticagrelor	1 week
Tirofiban	1 week
Abciximab	1 week

^a This is not a complete list. The treatment free period relative to Baseline should be at least 5 half-lives from last dose, but a minimum of 1 week, whichever is longer.

Prior/Concurrent clinical study experience

- 25. Study participant has previously received rozanolixizumab in another clinical study.
- 26. Study participant has participated in another study of an investigational IMP (and/or an investigational device) within the previous 30 days prior to the Screening Visit or within 5 half-lives prior to Baseline (whichever is longer) or is currently participating in another study of an investigational IMP (and/or an investigational device).
- 27. Criterion removed.

Diagnostic assessments

- 28a. Study participant has absolute neutrophil count <1500 cells/mm³ at the Screening Visit.
- 29. Criterion removed.
- 30. Study participant has a partial thromboplastin time ≥1.5x upper limit of normal (ULN) or International Normalized Ratio (INR) ≥1.5 at the Screening Visit.
- 31a. Study participant has 12-lead ECG with changes considered to be clinically significant upon medical review at Baseline.
- 32a. Study participant has renal impairment, defined as:

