6.4.3 Rescue therapy

Rescue treatment will be given as per standard of care and at the discretion of the investigator as described below. If such rescue therapy is given, the participant is allowed to continue IMP treatment (as per guidance below), and should continue to complete all remaining scheduled visits in the Treatment Period, as per the Schedule of Activities (Section 1.3). The following rescue therapies may be used:

- Any increase in concomitant ITP therapies above Baseline dose
- Any additional ITP medication/therapies including but not limited to:
 - Platelet transfusion (only in cases of severe bleeding)
 - Commercially available IVIg
 - Any systemically administered corticosteroids (above the background doses, ie, pulse, oral and iv steroids). Any systemic corticosteroids used for the management of infusion reactions or other medical conditions are also considered rescue therapy.
 - Immunosuppressants (except for those listed in Section 6.4.2).

Although the use of rescue therapy is allowable at any time during the study, the use of rescue therapy should be delayed, if possible, for at least 2 days following the administration of study treatment.

If IVIg, high dose corticosteroids, or platelet transfusion are given as rescue therapy, IMP treatment can commence at the same dose as previously when platelet counts are $<50 \times 10^9/L$. Dose can be up-titrated at a later timepoint, if needed, depending on platelet level.

A high dose of corticosteroids is defined as any iv administration of corticosteroids given for any reason or doubling of an oral dose resulting in a dose more than 20mg/day prednisone equivalent dose.

In case of an increase of Baseline oral corticosteroids, not resulting in doubling of the oral dose more than 20mg/day prednisone equivalent dose, an increase in the concomitant ITP therapies above Baseline, or in case of administration of immunosuppressants as rescue therapy, IMP administration can continue as per Schedule of Activities (Section 1.3) at a dose adjusted depending on the platelet level.

The date and time of rescue therapy administration as well as the name and dosage regimen of the rescue therapy must be recorded in the eCRF.

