7.2 Participant discontinuation/withdrawal from the study

Study participants are free to withdraw from the study at any time, without prejudice to their continued care. Participants who withdraw from the study should complete the EOS Visit.

A study participant may also be withdrawn from the study at any time at the discretion of the investigator for safety, behavioral, compliance, or administrative reasons.

If the study participant withdraws consent for disclosure of future information, the sponsor may retain and continue to use any data collected before such a withdrawal of consent.

If a study participant withdraws from the study, he/she may request destruction of any samples taken and not tested, and the investigator must document this in the site study records.

See the Schedule of Activities (Section 1.3) for data to be collected at the time of study discontinuation and follow up and for any further evaluations that need to be completed.

Study participants **must** be withdrawn from the study and permanently discontinued from IMP if any of the following events occur:

1. Study participant withdraws his/her consent.
2. Study participant takes prohibited concomitant medications as defined in this protocol.
3. Study participant meets the mandatory IMP discontinuation criteria as per Section 7.1.1, Section 7.1.2 or Section 7.1.3.

4. There is confirmation of a pregnancy during the study, as evidenced by a positive pregnancy test.
5. The sponsor or a regulatory agency requests withdrawal of the study participant.

Study participants who withdraw from the study or permanently discontinue IMP during the Treatment Period should complete the assessments outlined for the EW Visit, enter the SFU Period and complete the EOS Visit.

Investigators should contact the Medical Monitor, whenever possible, to discuss the withdrawal of a participant in advance. Study participants who are withdrawn will not be replaced.

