8.2.5 Time to first rescue therapy

Definitions:

Time to first rescue therapy (in days) is defined as: Date of first rescue therapy use - Date of first treatment + 1.

Participants who are withdrawn due to TEAEs will be censored at the start date of the TEAE, and participants who do not take rescue therapy will be censored at the date of withdrawal/study completion. Where there are several AEs which led to drop out, consider the earliest starting AE.

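### Anti-D, romiplostim and plasma exchange are prohibited without a rescue exception in Protocol 6.4.2 and 7.2 but fall within the open rescue wording of 5.2 and 6.4.3; if not ticked as rescue, such a use is censored in time to first rescue.

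*Protocol*

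**What the plan says.** Protocol 6.4.2 lists the prohibited treatments. Two entries carry a rescue exception: "IVIg (unless given as a rescue therapy") and "Any systemically administered corticosteroids above the allowed background dose (unless required as a rescue therapy"). Anti-D, romiplostim, plasma exchange (PEX), immunoadsorption, biologics including rituximab, cyclophosphamide, pimecrolimus and vinca alkaloids carry none. The stated consequence is: "The use of prohibited concomitant treatment will lead to permanent discontinuation from IMP". In 7.2, the second of the events requiring withdrawal from the study is: "Study participant takes prohibited concomitant medications as defined in this protocol".

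Protocol 5.2, criterion 24a, says that Table 5-1 medications "are prohibited during the study, unless required as rescue therapy", and refers to 6.4.3 for what counts as rescue. Table 5-1 lists anti-D, romiplostim and PEX under its heading for other therapies, not under immunosuppressants.

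Protocol 6.4.3 accepts as rescue: "Any additional ITP medication/therapies including but not limited to" a short list. That list names platelet transfusion, IVIg, systemic corticosteroids and immunosuppressants, the last with an exclusion for those in 6.4.2. A rescued participant may stay on IMP and is expected to attend the remaining treatment visits.

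SAP 6.6.2 identifies rescue by a CRF tick. SAP 6.6.1 summarises prohibited medication separately, from the 6.4.2 list. In SAP 8.2.5 the event is first rescue use, and "participants who do not take rescue therapy will be censored at the date of withdrawal/study completion". Table 8-5 lists two intercurrent events, TEAE withdrawal and COVID-19; withdrawal for a prohibited drug is not among them.

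**The concern.** A site that gives anti-D, romiplostim or PEX for falling platelets can follow criterion 24a and 6.4.3, record rescue and keep the participant on IMP. It can equally follow 6.4.2 and 7.2, stop IMP and withdraw the participant. The situation is foreseeable: Protocol 2.1 names anti-D and romiplostim among second-line options for ITP.

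For time to first rescue, a secondary endpoint, the label matters. If the site regards the drug as prohibited and does not tick rescue, the participant leaves the risk set at the moment treatment has failed. Kaplan-Meier assumes that a censored participant has the same future risk as those who remain, which is not so here, and the estimated rescue proportion is too low. The label also decides whether the use is an important protocol deviation (SAP 5.2 has a category for prohibited medication) and whether Week 25 data are collected.

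**Working it through.** **Step 1. Set the rules side by side by treatment.**

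| Treatment | Rescue exception in 6.4.2 | Group in Table 5-1 | Position under 6.4.3 | Result |
|---|---|---|---|---|
| IVIg | Yes | Other | Named | Consistent |
| Systemic corticosteroids above background | Yes | Not listed | Named | Consistent |
| Cyclophosphamide, pimecrolimus, vinca alkaloids | No | Immunosuppressants | Excluded, because listed in 6.4.2 | 6.4.2 and 6.4.3 agree |
| Rituximab and other biologics | No | Biologics | Not named; exclusion arguable for rituximab, which inclusion criterion 4b groups with immunosuppressants | Unclear |
| Anti-D, romiplostim, PEX | No | Other | Not named; inside the open wording, outside the exclusion | Conflict |

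**Step 2. Follow one use of a treatment in the last row through the SAP.**

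| Rescue ticked (6.6.2) | Withdrawn under 7.2 | Time to first rescue (8.2.5) |
|---|---|---|
| Yes | No | Event on the date of use |
| Yes | Yes | Event on the date of use; later withdrawal does not undo it |
| No | Yes | Censored at the withdrawal date |

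Only the third line produces the bias. No drug-level rule in the SAP prevents it.

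**Step 3. Size.** The plan gives no figure to reproduce. The SAP says 33 participants were randomized and the ratio was 2:1. The arm sizes are not stated, so assume 33 × 2/3 = 22 active and 33 × 1/3 = 11 placebo. One recoded use changes the crude rescue proportion by 1/22 = 4.5 points or 1/11 = 9.1 points. These denominators are participants, not events.

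SAP 8.2.5.1 uses Kaplan-Meier, S(t) = product of (1 − d/r), where d is the number of events and r the number at risk at each event time. An illustration with invented times, one ambiguous use on day 55 and participants without rescue followed to day 169:

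- Placebo, n = 11, other rescues on days 20, 30, 40, 50 and 60. Coded as an event: S = 5/11, rescue proportion 54.5%, median day 60. Coded as censored: S = 7/11 × 5/6 = 0.530, rescue proportion 47.0%, median not reached.
- Active, n = 22, other rescues every 10 days from day 20 to day 120. Coded as an event: S = 10/22, rescue proportion 54.5%, median day 110. Coded as censored: S = 18/22 × 10/17 = 0.481, rescue proportion 51.9%, median day 120.

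The Kaplan-Meier change differs from the crude share and depends on timing.

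**Step 4. Primary endpoint.** Rescue makes the participant a non-responder. Withdrawal for a prohibited drug is not a listed intercurrent event, but the missing platelet counts that follow are set to zero. The result is usually the same. It can differ under Protocol Table 9-1 for someone who already had 8 response weeks.

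**The case against.** The strongest answer is that the text partly resolves itself. Criterion 24a does not free every Table 5-1 drug; it defers to 6.4.3. Table 5-1 also lists anticoagulants such as warfarin and heparin, so a blanket exemption cannot be meant. Section 6.4.3 refers back to 6.4.2, and the two 6.4.2 entries with a rescue exception are also named in 6.4.3. One can read the specific list as governing the open phrase, so that the unmarked drugs are never rescue. This disposes of the claim that all Table 5-1 drugs are affected, and it settles cyclophosphamide, pimecrolimus and vinca alkaloids. It does not settle anti-D, romiplostim or PEX: the exclusion in 6.4.3 is confined to immunosuppressants, its opening phrase is unrestricted, and 24a expressly contemplates rescue use of drugs in their table.

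A reader might also infer that every such use becomes either a rescue event or a censored withdrawal. The SAP does not support that, because nothing makes the rescue and prohibited-medication summaries mutually exclusive; a ticked use counts even if the participant is then withdrawn.

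Finally, the trial was terminated, nobody was randomized under Amendment 3, and inference was dropped. All of that stands and limits the consequence. However, SAP 3.9 says the 33 were randomized under Amendment 2, and the amendment history dates the 24a cross-reference, the romiplostim prohibition and the discontinuation wording to that amendment. The wording therefore probably applied to the analysed participants.

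**Conclusion.** The concern holds in a limited form. For anti-D, romiplostim and PEX, Protocol 6.4.2 and 7.2 cannot be squared with 24a and 6.4.3 as written; for rituximab the position is arguable. The analysis consequence is informative censoring in time to first rescue, and it arises only when the drug is given for low platelets or bleeding, is not ticked as rescue, and withdrawal follows.

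The number of such uses is unknown and may be zero. The per-use figures rest on the assumed 22:11 split, and the Kaplan-Meier example on invented times. With arms this small, one recoded use can decide whether a median is reached, as the placebo example shows. A reader might infer a threat to confirmatory conclusions; there is none, since SAP 3.9 and 4.7 leave only descriptive summaries.

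**What to change.** The sponsor must reconcile Protocol 5.2 (24a), 6.4.2, 6.4.3 and 7.2 on which treatments may be given as rescue without withdrawal. Which rule is right is a clinical decision and is not proposed here. In a terminated study this cannot change conduct, but it would settle how recorded uses are classified.

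The change that affects the results is in SAP 6.6.2 and 8.2.5: count any ITP therapy listed in Protocol 6.4.2 and given for low platelets or bleeding as a rescue event on its start date, regardless of the CRF tick or later withdrawal. The uses can be found from the prohibited-medication summary in SAP 6.6.1, and start dates from the concomitant ITP treatment page cited in SAP 6.5.

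The cost is a short SAP addition and a review of the indication for each such use, preferably before unblinding. There may be slightly more rescue events.

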6.4.3 Rescue therapy

Rescue treatment will be given as per standard of care and at the discretion of the investigator as described below. If such rescue therapy is given, the participant is allowed to continue IMP treatment (as per guidance below), and should continue to complete all remaining scheduled visits in the Treatment Period, as per the Schedule of Activities (Section 1.3). The following rescue therapies may be used:

- Any increase in concomitant ITP therapies above Baseline dose
- Any additional ITP medication/therapies including but not limited to:
 - Platelet transfusion (only in cases of severe bleeding)
 - Commercially available IVIg
 - Any systemically administered corticosteroids (above the background doses, ie, pulse, oral and iv steroids). Any systemic corticosteroids used for the management of infusion reactions or other medical conditions are also considered rescue therapy.
 - Immunosuppressants (except for those listed in Section 6.4.2).

Although the use of rescue therapy is allowable at any time during the study, the use of rescue therapy should be delayed, if possible, for at least 2 days following the administration of study treatment.

If IVIg, high dose corticosteroids, or platelet transfusion are given as rescue therapy, IMP treatment can commence at the same dose as previously when platelet counts are $<50 \times 10^9/L$. Dose can be up-titrated at a later timepoint, if needed, depending on platelet level.

A high dose of corticosteroids is defined as any iv administration of corticosteroids given for any reason or doubling of an oral dose resulting in a dose more than 20mg/day prednisone equivalent dose.

In case of an increase of Baseline oral corticosteroids, not resulting in doubling of the oral dose more than 20mg/day prednisone equivalent dose, an increase in the concomitant ITP therapies above Baseline, or in case of administration of immunosuppressants as rescue therapy, IMP administration can continue as per Schedule of Activities (Section 1.3) at a dose adjusted depending on the platelet level.

The date and time of rescue therapy administration as well as the name and dosage regimen of the rescue therapy must be recorded in the eCRF.

